Why is this young population at such high risk for severe and permanent osteopenia and skeletal fragility? The onset of AN most frequently occurs during adolescence, a period of maximal bone accretion, with  $> 90\%$  of bone mass accrued by 18 years of age (11). Because adolescence is a critical time for attainment of peak skeletal mass, reduction of BMD during this crucial period may lead to long-term morbidity. Indeed, we found that in contrast to normal adolescents who demonstrate marked bone accretion during puberty, adolescents with AN do not increase their bone mass (12). Therefore, bone mass remains low in these girls during a critical period in normal bone development. We have previously shown that adults with onset of AN during adolescence have lower spine BMD than those with adult-onset AN, despite comparable years of amenorrhea (13). Furthermore, low bone mass in adolescents with AN may be permanent despite recovery (14). Approximately half of young women with AN have persistent osteopenia, even after  $>10$  years (15-17). Therefore, there may be a narrow “window-in-time” during adolescence in which maximal accrual of bone mass occurs and during which treatment paradigms to maximize bone accrual must be implemented.

The overall significance of this problem: A large number of adolescent girls suffer from anorexia nervosa resulting in major deficits in bone mass and increased skeletal fragility, which may be permanent. Our proposed study will 1) test the efficacy of replacing a deficiency of an

endogenous bone anabolic hormone, IGF-1, with estradiol as a unique therapy for the low bone formation state in adolescents with AN and 2) enable an understanding of the effects of this disease and its treatment by measuring not only compartment-specific changes in bone density, but microarchitecture and strength at weight bearing and non-weight bearing sites.

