(v) The Massachusetts Eating Disorders Association, which runs support groups for women and teenagers with eating disorders throughout eastern Massachusetts;

(vi) Health services at local colleges and universities such as Harvard University, Massachusetts Institute of Technology, Boston University, Boston College, Brandeis University, Emerson College, and Wellesley College

(vii) Facebook Advertisements. We also plan to use Facebook advertising to reach potentially interested subjects living in the Boston area. Women ages 18-45 living in New England will see advertisements for this research study in the "News Feed" section of their Facebook and be directed to an IRB approved RedCap prescreen survey. These advertisements will in no way be

designed to target individuals who indicate they may be struggling with an eating disorder on Facebook. The ads are shown to individuals based on the demographic requirements but have no link to any specific personal, profile or browsing history information. Examples of these advertisements are attached to this study protocol in Insight. A general Facebook page has also been created for this study (a Facebook requirement) and includes only basic contact and study information. A copy of this page is also attached to this study protocol in Insight.

(viii) Hasbro Children's Hospital at Rhode Island Hospital. We work with [name] and her team of providers to recruit subjects from Hasbro. This recruitment site will also function as an offsite clinic for follow up visits to provide Hasbro patients the opportunity to participate in the study with greater convenience. Subjects who are interested in the study can complete the eligibility portion of the screening visit at Hasbro and come to MGH for the consent process and baseline, 6 month, and 12 month visits. They will have the option to complete the entire 1, 3, 4.5, 7.5, 9, and 10.5 month visits at Hasbro.

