To maximize enrollment of adolescent subjects with AN, a number of referral mechanisms have been put into place over the past year that utilize the collegial relationships between [name], [name] and various directors of area eating disorder programs, as well as the Head of Child Psychiatry and major pediatric primary care practices. The investigators attend a monthly eating disorders support group at Walden Behavioral Care, which typically has an attendance of 70-80 patients, families, health professionals, and educators. The investigators also give talks on the endocrine and metabolic complications of AN to patients on the inpatient eating disorders units at Walden Behavioral Care, Center for Eating Disorders at Cambridge, Laurel Hill and HRI on a monthly or bi-monthly basis. Additionally, the Neuroendocrine Unit at Massachusetts General Hospital, in collaboration with the Harris Center, sponsors primary care symposia annually to educate the primary care clinician about eating disorders. These sessions also inform clinicians about research opportunities for eating disorder patients.

Control subjects will be recruited from pediatric practices at MGH, MGH-affiliated health care centers and community practices. Recruitment will occur through collaboration with physicians and caregivers at the above centers, and advertisement (i.e. posters, newsletters, and papers) in the community.

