Specific Aim 1B. We will analyze the impact of rhIGF-1 with estrogen (n=50) versus estrogen alone (n=50) on levels of the bone turnover markers, PINP and CTX, in girls with AN at 3, 6, 9 and 12 months using a repeated measures ANOVA. The primary planned analysis will be the difference in mean levels by treatment group during the 3, 6, 9 and 12 month observations. As for Specific Aim 1A, we will examine whether effects of combination therapy persist following discontinuation of therapy by examining these markers after 12 months of stopping therapy.

Specific Aim 1C. We will use the longitudinal model described above to compare the rate of bone mass accrual in girls with AN who receive rhIGF-1 with estrogen (n=50) with that seen in healthy controls (n=36). We expect the change in BMD in AN girls to exceed that in controls because of a “catch up” effect when rhIGF-1 is used with estradiol. We will control for multiple comparisons in our analysis when comparing against controls. Both unadjusted and multiplicity adjusted analyses will be presented.

Specific Aim 2A. In a cross-sectional design, we will compare the described HR-pQCT endpoints and bone strength (as assessed by FEA) in girls with AN (n=100) to those in healthy adolescents (n=36). We will use the Student t test when variables are normally distributed or when transformations can be performed to approximate a normal distribution; otherwise, we will use non-parametric tests such as the Wilcoxon rank sum test. Our preliminary data indicate lower trabecular bone density in 8 girls with AN compared with 6 controls (162 ± 27 vs. 209 ± 36 g/cm³, $p=0.02$). Based on these data, with 100 girls with AN and 36 controls in the study, we have >99% power for detecting a significant difference in trabecular bone density between the groups at an alpha level of 0.05. Another component of this specific aim is to determine the extent to which DXA parameters and possibly clinical parameters predict bone microarchitecture in the 100 adolescents with AN. This will help elucidate the role of DXA in the future clinical evaluation of adolescents with AN. Linear regression followed by regression modeling will be performed to determine hormonal, body composition, nutritional and exercise predictors of bone microarchitecture and bone strength in girls with AN and healthy adolescent girls.

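### Aim 2A compares AN girls with unmatched controls aged 14-22 by an unadjusted test; an age-adjusted model should be the planned comparison

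*SAP*

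**What the plan says.** SAP Specific Aim 2A compares the HR-pQCT endpoints and FEA bone strength between girls with AN and healthy adolescents. On the method it says: "We will use the Student t test when variables are normally distributed or when transformations can be performed". Where normality cannot be reached in that way, the fallback is stated as follows: "we will use non-parametric tests such as the Wilcoxon rank sum test". Power is given for trabecular density only, "with 100 girls with AN and 36 controls in the study", from a pilot of 8 AN girls and 6 controls ("162 ± 27 vs. 209 ± 36 g/cm³").

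No matching, stratification or covariate is stated for this comparison. The regression at the end of Aim 2A looks for hormonal, body composition, nutritional and exercise predictors of the bone measures. It names neither age nor bone age, and it is not an adjusted comparison of the groups. Pubertal maturation or status is named as a covariate only under Aims 1A and 2C.

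The Protocol (Research Design and Methods) sets the same limits for both groups: age 14-22 and bone age of at least 14. Age is therefore known for every subject, bone age is read from an x-ray, and height is measured at baseline. Background and Significance describes adolescence as "a period of maximal bone accretion" and reports the group's earlier AN-control comparison against controls matched on bone age, with height-adjusted BMD.

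**The concern.** The AN-versus-control contrast is observational. A shared eligibility range limits an age imbalance but does not remove it, and the range covers eight years in which, by the Protocol's own account, healthy girls are still gaining bone. Any difference in mean age between the groups passes straight into an unadjusted difference in means.

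An imbalance is plausible because the recruitment sources are not the same. AN sources include an adult eating-disorder center, advertising to women aged 18-45, and "Health services at local colleges and universities such as Harvard University". For the other group, "Control subjects will be recruited from pediatric practices at MGH", from affiliated and community practices, and by community advertisement.

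At stake is the estimate for every Aim 2A endpoint, and for endpoints with small true differences also the test result. The SAP gives an effect size for trabecular density alone, so nothing shows how the cortical, structural and strength endpoints would withstand such a bias.

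**Working it through.** **Inputs from the SAP (Aim 2A).** n = 100 and 36; pilot means 162 and 209; SDs 27 and 36 from 8 and 6 girls; alpha 0.05, taken as two-sided as in Aims 1A and 2B.

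**The plan's own figure.**
- Pooled SD = √[(7×27² + 5×36²)/12] = 31.07. Difference 47, or 47/31.07 = 1.51 SD.
- The pilot p value recomputes to 0.016 (pooled) or 0.025 (Welch), consistent with the stated 0.02, so the ± values are SDs.
- SE at 100 v 36 = 31.07 × √(1/100 + 1/36) = 31.07 × 0.194 = 6.04.
- 47/6.04 = 7.8 against a critical value of 1.98, so power exceeds 99.99%. The stated figure of over 99% reproduces, also with SD 27 or 36 and with unequal variances.

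**Assumptions not in the documents.** Within-group age SD 2.3 years (8/√12 = 2.31, used only as a scale), within-group correlation r of age with the endpoint 0.3-0.5, the same age slope in both groups, and a gap in mean age of 1-2 years.

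**Bias and rejection rate when there is no true difference.** Bias in SD units = r × gap / 2.31. The rejection rate comes from the noncentral t with 134 df and noncentrality bias/0.194.

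| r | Gap (years) | Bias (SD) | Two-sided rejection |
|---|---|---|---|
| 0.3 | 1 | 0.13 | 10% |
| 0.5 | 1 | 0.22 | 20% |
| 0.3 | 2 | 0.26 | 26% |
| 0.5 | 2 | 0.43 | 60% |

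For trabecular density this is 0.13 × 31.07 = 4.0 to 0.433 × 31.07 = 13.5 units, or 9-29% of 47. Even an 18-unit bias against a true difference of 47 leaves (47 − 18)/6.04 = 4.8 standard errors and power above 99%. For that endpoint the harm is a biased estimate, not a lost test.

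**What adjustment costs.** Adding age multiplies the SE by √(1 − r²) × √VIF, with VIF = 1 + p(1 − p) × gap², p = 100/136 and the gap in SD units. Example: gap 1 SD and r = 0.3 give VIF 1.195 and SE 6.04 × 0.954 × 1.093 = 6.30. Over gaps of 0-1.5 SD and r of 0-0.5, power for 47 units stays above 99%, and for half of that (23.5 units) it is 90-99%.

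**The case against.** - **The age gap is not shown.** AN girls are also sought through high schools, pediatric practices, a child psychiatry service and a children's hospital, and controls also through community advertising. The 18-45 range is an advertisement audience; eligibility stops at 22. The recruitment text available is not complete. A reader might infer that the AN group will be older, but the documents do not support that; they support only that age is uncontrolled.
- **The magnitude is assumed.** No age distribution or age-endpoint correlation is given. Background and Significance says that adolescents with AN fail to gain bone and that over 90% of bone mass is present by 18. Both suggest a flatter slope in much of the sample, and unequal slopes between groups. This stands, and it makes the table illustrative.
- **Direction.** A reader might infer that the unadjusted test inflates false findings of an AN deficit. That holds only if AN girls are younger (for a measure that rises with age). If they are older, false findings of a deficit fall to about 0.4%, 0.1% and 0.05% at biases of 0.13, 0.22 and 0.26 SD, below the nominal 2.5%; the excess is then AN appearing better, and a real deficit may be masked.
- **Importance.** Aim 2A is not a primary analysis. Both primary endpoints are randomized comparisons and are untouched. This stands and limits the priority.
- **Choice of covariate.** A single common slope may be wrong, and bone age may itself be affected by the disease. This shapes the remedy but does not defend leaving age out.

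**Conclusion.** The point holds as a gap in the analysis plan. Aim 2A makes a non-randomized comparison across an age span of bone accrual with no matching and no age term, although age is known for every subject. The text establishes that much. It does not establish that the groups will differ in age, or in which direction.

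The illustrative range (bias 0.13-0.43 SD, rejection rate 10-60% for an endpoint with no true difference) rests wholly on the assumed age SD, correlation, common slope and age gap. It should not be read as a forecast.

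Nor should the point be read as a challenge to the stated power: that figure reproduces, and the trabecular-density test would survive any bias considered here. The practical exposure is the size of the trabecular estimate, and both estimate and test for the other HR-pQCT and FEA endpoints if their true differences are smaller. The change is worth making mainly because it is nearly free.

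**What to change.** In SAP Specific Aim 2A, make the group comparison for each HR-pQCT and FEA endpoint a linear model with group and chronological age, with a transformation or robust standard errors where needed. Check a group-by-age term, because the Protocol itself suggests different age slopes; if it matters, report the group difference at stated ages. Keep the unadjusted t or rank-sum test as a supporting analysis, and tabulate age by group. Put bone age, and height for size-dependent measures such as cross-sectional area and strength, in sensitivity analyses, since the disease may affect skeletal maturity.

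The cost is SAP wording. No new measurement or subject is needed, age uses one of 134 degrees of freedom (two with the interaction), and power for the planned 47-unit difference stays above 99% over the range examined.

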Sample Size Determination: The study is powered to our primary endpoints, (i) change in lumbar spine BMD (specific Aim 1A), and (ii) change in trabecular bone density (specific Aim 3A) in girls with AN who receive estrogen and rhIGF-1 versus estrogen alone. **Specific Aim 1A:** The primary analysis for this Specific Aim and the study is to compare the change in BMD over time in subjects with AN randomized to receive rhIGF-1 and estrogen (n=50) with the corresponding change in estrogen treated subjects (n=50). Using data from our previous study, we found that the variance covariance matrix of the random effects model was as follows: variance-intercept 0.01056, variance-slope 0.001523, covariance -0.001, and the residual variance around each subject's trajectory 0.000533. Based on these parameters, with 100 subjects with AN (50 in each group), we will have an 80% chance of detecting a significant (p=0.05 two sided) difference in change in lumbar spine BMD between girls who receive estradiol and rhIGF-1 versus estradiol alone if the true difference in slope between the groups is 0.03 g/cm²/year. This is a medically significant difference in that lumbar spine BMD in adolescents with AN is about 0.08 g/cm² lower than that in healthy adolescents at baseline. Estradiol alone has a net effect of 0.02 g/cm².year in increasing bone density, so an additional effect of 0.03 g/cm² (with rhIGF-1) added to 0.02 g/cm² (from estradiol alone) would be a net effect of 0.05 g/cm²/year (from estradiol and rhIGF-1). This would allow girls with AN to catch up to healthy adolescents. The sample size calculation, which assumes a 20% dropout rate, is based on the methods described by Yi and Panzarella (38) using the program <http://hedwig.mgh.harvard.edu/biostatistics/node/35>. The same model can be used with covariates and possible mediators of treatment effects such as baseline nutritional status, body composition, hormonal status, exercise and pubertal maturation. We will also explore the possibility that effects of rhIGF-1 with estradiol persist after discontinuation of treatment by examining bone density 12 months after stopping therapy.

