Specific Aim 2B. The goal of this specific aim is to determine prospectively changes in bone microarchitecture and bone strength in girls with AN who receive rhIGF-1 and estrogen therapy (n=50) compared with changes in AN receiving estrogen alone (n=50). Bone microarchitecture will be assessed using HR-pQCT and bone strength using FEA at baseline, six, 12 and 24 months of the study. Our second primary study endpoint is the change in trabecular bone density in the two treatment groups over the course of the study. With 100 subjects (50 in each group) we will have an 80% chance of detecting a significant difference ($p=0.05$ two sided) in change in trabecular bone density in girls with AN who receive rhIGF-1 and estrogen compared with estrogen alone if the true relative change is 3.5% over the 12 month period. This assumes a standard deviation of relative change of 6%, as was found in the group of AN women who gained weight in a study by Milos *et al* (39). To understand the clinical meaning of such a change we note that AN women had a 20% decrease in trabecular bone density compared to normal women. The analysis will be accomplished using a longitudinal mixed model ANOVA with a random patient and time (slope) effect. The measure of interest will be the group time interaction. We estimate a 20% dropout rate based on our previous study. A secondary analysis will be a joint model with weight gain as described for Specific Aim 1. We will also compare changes in total cross-sectional area, cortical thickness, TbN, TbTh and TbSp between AN receiving rhIGF-1 and estrogen with AN receiving estrogen alone. Although this is not a specific aim, it will be interesting to compare the changes in BMD with the change in bone strength. An issue is that BMD and bone strength are measured in different units. In order to make the comparisons understandable, we will transform both to percent predicted using the data from healthy adolescent girls. Then we will fit a joint model for both measurements to assess the relationship between the two and which measure is affected most by treatment. In addition, we will examine these endpoints 12 months after stopping therapy to determine whether effects persist after discontinuing combination therapy. When comparing with healthy adolescent girls, we will adjust for multiple comparisons. Both unadjusted and multiplicity adjusted analyses will be presented.

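### The two primary endpoints have no joint testing rule; trabecular density also lacks a named HR-pQCT site and a clear time point, and its 80% power rests on unstated dropout assumptions

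*SAP*

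**What the plan says.** **Endpoints.** SAP, Sample Size Determination, opens with "The study is powered to our primary endpoints" and lists two: change in lumbar spine BMD (Aim 1A) and change in trabecular bone density (labelled Aim 3A there, but described under Aim 2B). The Aim 1A text calls the BMD comparison the primary analysis of the study. Aim 2B says "Our second primary study endpoint is the change in trabecular bone density". Each is given a two-sided 0.05 level.

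**Multiplicity.** Aim 1C says "We will control for multiple comparisons in our analysis when comparing against controls". Aim 2B says "When comparing with healthy adolescent girls, we will adjust for multiple comparisons". Nothing comparable is said about the two randomised arms.

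**Site and time point.** The protocol (Specific Aims; Baseline Visit, item (o)) has HR-pQCT at the ultradistal radius and the distal tibia, and separates them as non-weight-bearing and weight-bearing bone. Aim 2B names no site. It defines the endpoint over the whole study, with scans at baseline, 6, 12 and 24 months, but its power statement is for 12 months.

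**Power.** Aim 2B states "With 100 subjects (50 in each group) we will have an 80% chance of detecting a significant difference" for a 3.5% difference in relative change. "This assumes a standard deviation of relative change of 6" percent gives the variability. Some sentences later comes "We estimate a 20% dropout rate based on our previous study", with no link to the 80%. The model is given as "The analysis will be accomplished using a longitudinal mixed model ANOVA with a random patient and time (slope) effect". The Aim 1A text says that the sample size calculation assumes 20% dropout.

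**The concern.** Two tests at full level, one of them on an outcome measured at two sites, leave open what may be claimed if only one is significant. Calling BMD the study's primary analysis and trabecular density the second primary endpoint hints at an order. It does not say whether a trabecular result may be claimed when BMD fails, or which site and scan decide it. Fixing these after the data are seen would undermine a single positive result.

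On power, 20% dropout from 50 per arm leaves 40. The SAP does not say whether the 80% is before or after that loss, so a reader of a null trabecular result cannot set it against a documented power.

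**Working it through.** **1. The stated power, as a comparison of two means.** Inputs from SAP Aim 2B: difference 3.5, SD 6, two-sided 0.05.

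Power (normal) = Φ(3.5 / (6·√(2/n)) − 1.960).

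| n per arm | 3.5 / (6·√(2/n)) | Power, normal | Power, noncentral t |
|---|---|---|---|
| 50 (no dropout) | 2.917 | 83.1% | 82.3% |
| 40 (50 × 0.8) | 2.609 | 74.2% | 73.1% |

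Neither row gives 80%. The n that does is 2·((1.960 + 0.8416)·6/3.5)² = 46.1, so 47 per arm (normal) or 48 (t). That is about 4-6% loss from 50. With 40 per arm, the difference detectable at 80% is 6·√(2/40)·2.8016 = 3.76% (normal) or 3.81% (t).

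**2. The planned mixed model, which keeps partial data.** The SAP gives no HR-pQCT variance components, so assumptions are needed:
- Scans at 0, 6 and 12 months; 40 per arm with all three and 10 dropouts.
- Aim 1A's components (intercept 0.01056, slope 0.001523, covariance −0.001, residual 0.000533), rescaled so that the 12-month change has SD 6. The factor is 36 / (0.001523 + 2 × 0.000533) = 13,905, and the residual share of that variance is 41%.
- Power from the generalised least squares variance of the group-by-time slope, with separate group baselines.

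| Dropouts leave | Aim 2B (rescaled) | Aim 1A (own components, 0.03 g/cm²/year) |
|---|---|---|
| all before month 6 | 74.9% | 75.8% |
| half before, half after | 76.8% | 77.7% |
| all after month 6 | 78.6% | 79.5% |

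With zero covariance, residual shares of 2-60% and the same three timings, Aim 2B runs from 74.2% to 82.6%. A model with one common baseline mean, on the rescaled components, gives 77.7%, 79.9% and 81.8%.

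**3. Error rate if more than one result could support a claim.** The correlations are assumed; the documents give none.
- BMD or trabecular density: 1 − 0.95² = 9.75% if independent; 9.1% at correlation 0.5; 7.8% at 0.8.
- BMD or either HR-pQCT site: 1 − 0.95³ = 14.3% if independent; 9.8% if all correlations are 0.8.
- BMD tested first, BMD truly responding, trabecular density not, and a free choice of site: again two tests, so about 8-10%.

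**4. Cost of a rule.** Both effects as designed, mixed-model powers from step 2, correlation 0-0.8, simulated bivariate normal:

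| Rule | BMD claim | Trabecular claim | Trabecular claim if BMD has no true effect |
|---|---|---|---|
| Each at 0.05 | 76-80% | 75-79% | 75-79% |
| Holm | 71-77% | 70-76% | 65-70% |
| BMD first, fixed order | 76-80% | 57-72% | at most 4% |

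**The case against.** A reader might infer from 73-74% that the trial is underpowered, or that a shortfall is likely. The documents do not support that. The Aim 1A sentence on 20% dropout sits in a section that opens with both endpoints, so it may cover both. The completer figure ignores the month-6 scans of girls who leave later. The stated 80% lies inside the 74-83% mixed-model range, and Aim 1A, which says it includes dropout, gives 76-80% by the same method. The SD is itself borrowed from women with AN who gained weight: moving it to an assumed 5.5 or 6.5 shifts power at 50 per arm to 89% or 77% (normal), as large as the gap in question. What stands is that the assumption behind the 80% is not written down.

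A reader might also infer that the plan runs at a 10-14% error rate. That holds only if success on either endpoint, or at either site, would be claimed, and the SAP says neither that it would nor that it would not. The wording does lean towards BMD first. What stands is that a leaning is not a rule, and that even a BMD-first order leaves the site open.

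Finally, a BMD-first order is not the obvious remedy. The protocol's Background and Significance says that DXA-derived BMD reflects fragility in AN poorly, which argues against letting it gate the HR-pQCT endpoint.

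**Conclusion.** The concern holds on two counts.

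1. **Testing rule, site and time point.** The gap is plain from the text and needs no modelling. Its size is conditional: about 8-10% familywise error if either endpoint could support a claim, and about 10-14% if either site could also count, under assumed correlations of 0 to 0.8. The site and time-point gaps concern trabecular density only.
2. **Power.** The 80% in Aim 2B is not reproduced by its stated inputs, which give 82-83% without dropout and 73-74% on completers. Under the planned model it is attainable for some combinations of dropout timing and residual variance. This is missing documentation, not a demonstrated error. The mixed-model range rests on scans at 0, 6 and 12 months and on assumed variance components.

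Both should be fixed before unblinding.

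**What to change.** 1. **Endpoint.** Name one HR-pQCT site and the 12-month change as the second primary endpoint. Make the other site and later scans secondary. Correct the Aim 3A label to 2B.
2. **Testing rule.** State one rule that holds the two-sided 0.05 level across the two primary endpoints. The choice is the sponsor's:
   - *Holm* keeps trabecular density claimable if BMD fails, at about 3-5 points of power for each endpoint.
   - *Fixed order, BMD first* leaves BMD power unchanged but allows no confirmatory trabecular claim if BMD fails; that claim falls to 57-72% when both effects are as designed.
3. **Power.** Restate Aim 2B as 82-83% with 50 per arm and no dropout, and 73-74% on 40 completers per arm after 20% dropout (detectable difference about 3.8% at 80% power). Add that mixed-model power depends on dropout timing and variance components. If the 80% already included dropout, state instead the HR-pQCT variance components and dropout timing used. Do not present the two figures as bounds on mixed-model power: a common-baseline model with small residual variance and late dropout can exceed the upper one. Do not enter a figure borrowed from the DXA components.

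The cost is SAP wording, a less favourable power statement unless the original calculation is documented, and the power given up under the chosen rule. Enrolment, visits and model stay as they are.
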